6.1.3. Double-Blind Phase

Subjects who are stabilized and responding to their CAM2038 q1w dose (4, 8, 12, 16, 24, or 32 mg/week) at the end of the Titration Phase and who fulfill the pre-defined randomization criteria will be randomized to one of two treatment groups in the 12-week Double-Blind Phase:

- Group 1: CAM2038 q1w or CAM2038 q4w SC injections
- Group 2: placebo q1w or placebo q4w SC injections

During the Double-Blind Phase, all subjects who are receiving 4, 8 or 12 mg CAM2038 q1w at the end of the Titration Phase will be randomized to continue their respective CAM2038 q1w dosing of 4 mg, 8 mg or 12 mg CAM2038, or to matching placebo q1w for a total treatment duration of 12 weeks. Subjects who are receiving 16 mg, 24 mg or 32 mg CAM2038 q1w at the end of the Titration Phase will be randomized to CAM2038 q4w (64 mg, 96 mg or 128 mg, respectively) or to matching placebo q4w for a total treatment duration of 12 weeks.

Figure 1: Overview of Study Design

¹ One booster is allowed on Day 3-5 after the first CAM2038, 4 or 8 mg injection. If booster is taken, the next dose on week 2 will be 8 or 12 mg, otherwise stay at 8 mg. Then titration is weekly up to 10 weeks. Final Study Visit is 1 week after the last CAM2038 q1w dose for q1w subjects and 4 weeks after the last q4w dose for q4w subjects. Follow-up is within 4 weeks after the Final study visit.

IR = immediate release; MED=morphine equivalent dose; q1w=once weekly; q4w=once monthly; R= randomization. There will be a Final Study Visit or Early Termination and one Follow-up Call.

Rescue medication, hydrocodone/acetaminophen 5 mg/325 mg q4-6h prn, will be allowed during the Double-Blind Phase (up to three tablets or 15 mg/975 mg/day for subjects whose MED at screening was between 40-79 mg/day and up to six tablets or 30 mg/1950 mg/day for subjects whose MED at screening was ≥80 mg/day). Whenever subjects take rescue medication, they must record their pain intensity “at that moment” prior to taking rescue medication in the electronic diary.

6.1.4. Follow-up Phase for Subjects Not Transitioning to the Open Label Safety Extension Phase

A Final Study Visit will take place 1 week after the last CAM2038/placebo q1w dose or 4 weeks after the last CAM2038/placebo q4w dose. At the Final Study Visit (or early termination), subjects will be transitioned back to standard care or to their treatment prior to study entry. Subjects will then be contacted

at Follow-up, within 4 weeks after the Final Study Visit, to assess AEs and concomitant medications.

Subjects transitioning from the Randomized Double-Blind Phase to the Open Label Safety Extension Phase are encouraged to do so at the Final Study Visit of the randomized Double-Blind Phase or as soon as possible thereafter.

6.1.5. Open Label Safety Extension

Subjects who complete the Double-Blind Phase will be offered the opportunity to continue treatment in an open label safety extension for a total duration of up to 60 weeks. Subjects who consent to the Open Label Extension will not be required to participate in the post-double-blind Follow-up Phase but will be transitioned at their Final Study Visit or as soon as possible thereafter, to open label active treatment, in the Open Label Extension. With the Open Label Safety Extension Phase, total duration of exposure to CAM2038 is up to 60 weeks. Enrollment in the Open Label Safety Extension Phase will continue until a sufficient number of subjects have been recruited to obtain at least 52 weeks of safety information in approximately 100 subjects. Due to the double-blind design, all subjects will need to receive at least 1 week of CAM2038 q1w before proceeding to the Open Label Safety Extension Phase.

Subjects completing the Double-Blind Phase on 4 mg, 8 mg or 12 mg CAM2038/placebo q1w will continue on the same dose of active treatment (open-label CAM2038) without need for titration. Subjects completing the Double-Blind Phase on 64 mg, 96 mg or 128mg CAM2038/placebo q4w will begin open-label treatment at the corresponding equivalent weekly dose last received by the subject prior to transition to the monthly dosing regimen. The subject may transition to monthly dosing upon return to the clinic in 1 week following the initial dose. At the Investigator's discretion, the transition period may be extended or the patient down-titrated, in case of poor tolerability. The subjects will continue in the Open Label Safety Extension Phase until the total exposure to CAM2038 (including the Titration and Double-Blind Phases) is at least 52 weeks.

Once the required number of subjects for the Double-Blind phase of the trial has been recruited, enrollment for the Double-Blind phase will be closed, and remaining subjects offered the opportunity to proceed directly to the long-term safety extension without having to participate in a double-blind treatment phase. However, to be eligible to proceed to the safety extension, subjects must meet the following criteria:

- Have CAM2038 titrated to a dose that provides analgesia (i.e., 7-day mean $API \leq 4$)
- The dose of CAM2038 is well-tolerated for 7 days before randomization (no adverse effects that require a change in study dosing or interruption)
- Subject does not require, on average, more than one dose of rescue medication per day over the previous 7 days

The opening of recruitment of subjects for the safety extension is to ensure that a sufficient number of subjects are enrolled to provide required long-term safety data to support the clinical development of CAM2038 for the indication of chronic pain requiring daily treatment with opioids.

These so called "de novo" subjects may have CLBP or other severe chronic pain disorders (such as osteoarthritis) and will not be required to participate in the Double-Blind Phase. The de novo subjects will undergo the same screening procedures, down titration, morphine IR and CAM2038 up-titration as required for subjects going through the Double-Blind Phase of the study. The CAM2038 dosing titration and rescue medication requirements for the safety extension for subjects whose opioid doses at screening

are > 80 mg/day MED, and 40-79 mg/day MED, respectively, shall be the same as described for the subjects participating in the Double-Blind Phase. De novo subjects may also be subjects who have completed the core study more than 28 days ago or newly identified subjects with a chronic pain indication treated with daily opioids.

Subjects in the Open Label Safety Extension Phase will return to the study clinic for their regular weekly or monthly CAM2038 injections until the end of the study. At the Month-4 safety extension visit (Visit Week 23 for de novo subjects and Visit Weeks 35-36 for subjects transitioned from randomized Double-Blind Phase), PK sampling for CAM2038 steady state PK will be performed on all subjects who provide additional consent for the PK sampling. Blood samples will be collected prior to administration (within 45 minutes); and at approximately 2 hours, 6 hours, 24 hours, 72 hours, 168 hours, 336 hours, and 672 hours after administration to measure plasma levels of BPN and norBPN for subjects receiving both CAM2038 qlw and CAM2038 q4w treatments. Actual dates and times of dosing of IMP during the safety extension phase, as well as, blood sampling for PK measurement will be recorded.

The study design schematics for the Open Label Safety Extension Phase are presented in **Error! Reference source not found.** and Figure 3 below.

Figure 2: Overview of Open-Label Extension for Subjects Continuing from Double-Blind Phase Study²

Screening	Down Titration		Buprenex Test Dose & Transition to CAM2038	CAM 2038 q1w Titration Phase ¹	CAM 2038 q1w/q4w Randomized	Titration Phase	CAM 2038 q1w/q4w Open Label extension	Follow up
≥40 mg MED	Titration from previous opioid to ≤ 40 or 80 MED	IR morphine for at least 2 days prior to Day 1	Test Dose of Buprenex	Subjects will be titrated to effective analgesic dose of CAM 2038 q1w	
R
		Active Rx CAM2038 q1w and CAM2038 q4w	For Concomitant Medications and AEs
			First dose of CAM2038 q1w 4 mg (pts with screening MED 40-79) 8 mg (pts with screening MED ≥80)	Subjects may be randomized after 2 consecutive weeks of analgesia at a constant CAM2038 dose regimen				
2 weeks	2 weeks		1 day	Up to 10 weeks	12 weeks	1 week	Up to 36 weeks	Up to 4 weeks

¹ One booster is allowed at the discretion of the investigator, on Day 3-5 after the first 4 or 8 mg injection CAM2038 for subjects experiencing significant pain. Then titration is weekly up to 10 weeks. Follow up is within 4 weeks after the Open Label Treatment Phase

² Figure 2 represents entire participation of subjects, who continue on from the randomized double blind of the study through the extension. However, subjects will not be required to participate in the Double-Blind Phase follow-up period and may proceed directly into the Open-Label Safety Extension Phase. A maximum gap of 28 days is allowed between the end of the Double-Blind Phase and the start of the Open-Label Safety

Extension Phase

Figure 3: Overview of Open Label Extension for De Novo Subjects

Screening	Down Titration & IR Morphine		Buprenex Test Dose	Transition to CAM2038 First Dose	CAM 2038 q1w UP-Titration Phase ¹	CAM 2038 q1w or q4w Active Open Label Treatment	Follow up
Subjects on 40-79 mg MED	Titrate from previous opioid to ≤ 40 or 80 MED	IR morphine for at least 2 days prior to Day 1	Test Dose of Buprenex	4 mg CAM2038 -For subjects with opioid MED of 40-79 mg at screening	Subjects will be titrated to an effective analgesic dose of CAM2038 q1w	CAM2038 q1w (4, 8, or 12 mg)	Safety follow-up for AEs & ConMeds
Subjects on > 80 mg MED				8 mg CAM2038 -For subjects with opioid MED ≥80 mg at screening	Subjects may be enrolled into Open Label Extension after 2 consecutive weeks of analgesia at a constant dose regimen	OR CAM2038 q4w (64, 96, 128 mg)	
2 weeks	2 weeks		1 day		Up to 10 weeks	Up to 50 weeks	up to 4 weeks

¹ One booster is allowed at the discretion of the investigator, on Day 3-5 after the first 4 or 8 mg injection CAM2038 for subjects experiencing significant pain. Then titration is weekly up to 10 weeks. Follow up is within 4 weeks after the Open Label Treatment Phase.

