1. After at least a 12-hour washout from the last IR morphine dose, subject must have a COWS ≥ 5 and an API pain score over the past 24 hours ≥ 5 in order to receive a test dose of Buprenex.
2. Passed all baseline criteria, including a normal QTcF, had no change in QTcF > 30 ms at 1 hour after the test dose with Buprenex, and had a COWS score < 5 after the test dose with Buprenex.

Note:

- Subjects on BPN at Screening are required to participate in the down titration and will undergo a washout period prior to the test dose and first on-study treatment. Subjects entering the study on BPN will not transition to IR Morphine, but will refrain from taking their BPN for 12 -24 hours prior to the test dose to achieve the desired washout period.
- Subjects on BPN at Screening are still required to follow the same Day 1 procedures (e.g., confirmation of pain scores, COWS assessment and Buprenex test dose) as non-BPN subjects.

Criteria for Randomization into the Double-Blind Phase:

1. Been on a stable dose of CAM2038 q1w for at least 2 consecutive weeks.
2. CAM2038 titrated to a dose that provides analgesia (i.e., 7-day API score of ≤ 4 and at least 2 points below the value at the start of Titration Phase) and is well tolerated for 7 days before randomization.
3. Requires no more than an average of one hydrocodone/acetaminophen 5 mg/325 mg/day during the last 7 days prior to randomization.
4. Demonstrated study medication (CAM2038) compliance $\geq 80\%$ during the previous 14 days.
5. Demonstrated daily compliance with pain intensity scoring for ≥ 11 of the previous 14 days, including the last 3 days prior to randomization.

Inclusion Criteria for Open Label Extension

For Subjects Continuing from The Randomized Double-Blind Phase.

Subjects must have:

1. Completed Double Blind Phase of the study
2. Signed Informed Consent for Safety Extension

Subjects completing the double-blind phase will be enrolled directly into the open label extension at their respective dose level of CAM2038. They will not be required to participate in a Buprenex treatment test dosing or participate in a titration phase.

For De Novo Subjects (New Subjects Recruited Directly into The Open Label Extension)

Subjects who are not participating in the Double-Blind Phase of the Study must meet all of the following inclusion criteria in order to be eligible for participation in the study:

1. Written informed consent provided prior to the conduct of any study-related procedures.

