8.1.7. Open Label Safety Extension

Once the required number of subjects for the Double-Blind phase of the trial has been recruited (approximately 340), enrollment for the Double-Blind Phase will be closed and remaining subjects with CLBP will be offered the opportunity to proceed directly to the Open Label Safety Extension Phase without having to participate in the Double-Blind Phase. However, to be eligible to proceed to the Open Label Safety Extension Phase, subjects must meet the following criteria:

- The analgesic dose of CAM2038 is well-tolerated for 7 days before entry into open label study (no adverse effects that require a change in study dosing or interruption)

The opening of recruitment for subjects with CLBP for the safety extension only after enrollment for the randomized Double-Blind Phase of the study is complete, is to ensure that eligible subjects with CLBP are enrolled into the pivotal randomized Double-blind phase first. However, other subjects with chronic pain requiring daily treatment with opioids, who do not qualify for the randomized Double-Blind Phase of the study but are eligible for the safety extension phase may be enrolled directly into the safety extension phase (so called de novo subjects). These subjects will not be required to wait for recruitment for the randomized Double-Blind Phase to be completed prior to enrolling into the safety extension. The purpose of the safety extension is to ensure that sufficient data is obtained, to provide at least 52 weeks of exposure safety information in at least 100 subjects. These long long-term safety data are required to support the clinical development of CAM2038 for the indication of chronic pain requiring daily treatment with opioids.

De novo subjects proceeding directly to the open label extension, will undergo the same screening procedures, down titration, morphine IR, Buprenex test dose, and CAM2038 up-titration similar to the requirement for subjects enrolling into the randomized Double-Blind Phase of the study. The CAM2038 dosing titration and rescue medication requirements for the safety extension for subjects whose opioid doses at screening are > 80 mg/day MED, and 40-79 mg/day MED, respectively, shall be the same as described for the subjects participating in the Double-Blind Phase.

Subjects in the safety extension will return to the study clinic for their regular weekly or monthly CAM2038 injections until the end of the study.

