8.1.7.1. Dosing Schedule

The dose titration schedule below provides guidance regarding titration of subject dosing upon enrollment into the open label extension portion of the study following participation in the double-blind randomization.

- All subjects will be started on the weekly CAM2038 regimen during the open label extension.
- Subjects completing the randomized double-blind phase on 4 mg, 8 mg, or 12mg CAM2038/placebo q1w will continue the same dose of active treatment (open label CAM2038) without need for titration.
- Subjects completing the randomized double-blind phase on 64 mg, 96mg, or 128mg CAM2038/placebo q4w will begin open label treatment at the corresponding equivalent weekly dose last received by the subject prior to transition to the monthly dosing regimen. The subject may transition to monthly dosing upon return to the clinic in 1 week following the initial dose. At the investigator’s discretion, the transition period may be extended or the patient down-titrated, in case of poor tolerability.
- Additional details are presented in [Table 4](#) below:

Table 4 Open-Label Extension Dose Schedule for Randomized Double-Blind Rollover

Randomized Double-Blind Dose	Titration Schedule
4mg CAM2038 q1w	Remain at 4mg weekly
8mg CAM2038 q1w	Remain at 8mg weekly
2mg CAM2038 q1w	Remain at 12mg weekly
64mg monthly*	Start at 16mg q1w
96mg monthly*	Start at 24mg q1w
128mg monthly*	Start at 32mg q1w

*Please note:

- 16 mg CAM2038 q1w is the dosing equivalent of 64 mg CAM2038 q4w
- 24 mg CAM2038 q1w is the dosing equivalent of 96 mg CAM2038 q4w

- 32 mg CAM2038 q1w is the dosing equivalent of 128 mg CAM2038 q4w

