8.4. Selection of Dose

The study will include the following doses based on each subject's individual analgesia needs and tolerability:

- CAM2038 q1w 6.25 mg/mL: 4 mg (BPN base); 0.64 mL SC injection
- CAM2038 q1w 50 mg/mL: 8 mg, 12 mg, 16 mg, 24 mg, and 32 mg (BPN base); 0.16, 0.24, 0.32, 0.48, and 0.64 mL SC injection
- CAM2038 q4w, 356 mg/mL: 64 mg, 96 mg, and 128 mg (BPN base); 0.18, 0.27, and 0.36 mL SC injection.

Dose adjustments will be allowed during the Open Label Titration Phase only.

Rescue medication is oral hydrocodone/acetaminophen, 5 mg/325 mg tablets, q4-6 h prn. The maximum daily dose is 30 mg/1950 mg/day. Subjects cannot take more than one rescue tablet per day, on average, in the week prior to randomization.

On Day 1 of the Titration Phase, subjects will receive a test dose consisting of a single IM injection of 0.30 mg (1.0 mL) Buprenex and will be assessed for any changes in QTcF or withdrawal prior to any administration of CAM2038.

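### Blinded placebo completers restart CAM2038 at their last titration dose about 13 weeks after their last active injection, and the only written dose reduction comes after a depot has been given

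*Protocol*

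**What the plan says.** **Restart dose.** Protocol 6.1.5 and 8.1.7.1 state that subjects finishing on 64, 96 or 128 mg monthly, active or placebo, "will begin open-label treatment at the corresponding equivalent weekly dose last received by the subject prior to transition to the monthly dosing regimen". Table 4 gives these doses as 16, 24 and 32 mg weekly. Subjects finishing on 4, 8 or 12 mg weekly, active or placebo, "will continue the same dose of active treatment (open label CAM2038) without need for titration". The synopsis agrees: "Subjects completing the double-blind phase will be enrolled directly into the open label extension at their respective dose level of CAM2038". It then waives both the Buprenex test dose and a titration phase for these subjects. No rule separates the arms, and Section 8.2.6 keeps site staff blinded (other than the pharmacist and the injecting staff) until the sponsor unblinds the study.

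**Lowering the dose.** At the investigator's discretion "the transition period may be extended or the patient down-titrated, in case of poor tolerability". In 8.1.7.1 this sits inside the bullet for the monthly stratum; in 6.1.5 it follows the text on that stratum. Section 8.4 states a general limit: "Dose adjustments will be allowed during the Open Label Titration Phase only".

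**Text that softens this.** Section 8.1.7.1 introduces its schedule as guidance. Section 6.1.5 requires at least a week of weekly dosing before the extension proper. Section 7.5.2 lets the investigator exclude a subject on safety grounds.

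**The concern.** One restart rule is applied to subjects in very different states. An active completer has had continuous buprenorphine. A placebo completer has had none for about three months, with rescue hydrocodone as the only opioid the study supplied. Section 9.5 describes the drug as very potent and its doses as selected for opioid-experienced subjects. Section 8.1.3 starts subjects at 4 or 8 mg and then adjusts weekly.

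An investigator who does not know the arm, facing a subject with little recent opioid intake, finds no written option to begin below the previous dose. The written remedy presupposes that a long-acting depot is already in place. Safety is the primary objective of the extension (Section 5.3.1), so its first dose deserves a clear rule.

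**Working it through.** **Inputs.** Weekly titration injections to nominal Week 10 (Table 5). Double-blind injections at Weeks 11 to 22 weekly (Table 6) or Weeks 11, 15 and 19 monthly (Table 7). First open-label dose, a weekly depot, at Week 23 (Tables 8a and 8b). Permitted gap before rollover of 28 days (Figure 2 footnote). Visit windows of ±3 days in titration, and ±3 days (weekly) or ±7 days (monthly) in the Double-Blind Phase. Rescue cap of 3 or 6 tablets of 5 mg hydrocodone (6.1.3, 8.1.4). Oral hydrocodone 30 mg = oral morphine 30 mg (Table 3). Buprenorphine-to-morphine factor of 50 (4.3).

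**Days since last active injection at Week 23.**
- Placebo: (23 − 10) × 7 = 91. A shorter titration gives the same result, because it is always 1 week to the first placebo injection plus 12 weeks on placebo.
- Active weekly: (23 − 22) × 7 = 7.
- Active monthly: (23 − 19) × 7 = 28.
- Placebo with the full permitted gap: 91 + 28 = 119.
- Placebo with visit windows drifting in opposite directions (assumption): 91 ± (3 + 3) = 85 to 97 for the weekly stratum; 91 ± (3 + 7) = 81 to 101 for the monthly stratum.

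**Study opioid on placebo.** 3 × 5 = 15 mg and 6 × 5 = 30 mg hydrocodone a day, which Table 3 makes 15 and 30 mg morphine equivalents. Both are below the 40 mg a day in Section 9.5. Sections 8.1.6 and 8.4 state a single cap of 30 mg, which leads to the same conclusion.

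**Size of the restart dose.** The plan's own figure first: 4 / 7 × 50 = 28.57 mg a day, against 28.5 stated in Section 4.3, so it reproduces. The same formula gives:

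| Weekly dose (mg) | Morphine equivalents (mg/day) |
|---|---|
| 4 | 28.6 |
| 8 | 57.1 |
| 12 | 85.7 |
| 16 | 114.3 |
| 24 | 171.4 |
| 32 | 228.6 |

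The highest first injection in titration is 8 mg (8.1.3), so a 32 mg restart is 32 / 8 = 4 times that. If the optional second injection in the first week is counted (8 + 8 = 16 mg), it is 32 / 16 = 2 times the first-week total. These ratios describe dose size. They do not predict harm.

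**The case against.** **The restart dose is not arbitrary.** Section 7.4 requires at least two stable weeks on it and seven days of good tolerability before randomisation. Section 4.2 cites a ceiling on respiratory depression and Section 4.1 a minimal initial burst. Week 23 has vital signs, with respiration rate and pulse oximetry, before and 1 hour after dosing. All of this stands and keeps the point minor.

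**The text leaves some room.** Guidance is not a prohibition, and saying titration is not needed does not forbid it. Figure 2 even shows a one-week titration column before the extension. Section 8.4 read literally would also cancel the extension's own down-titration, so the specific text probably governs. This is fair, and it means the protocol does not forbid a lower start. Still, the only reduction it describes is reactive, and sites are left to reconcile 8.4, Figure 2 and the synopsis themselves.

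**A 28-day re-titration clock.** A reader might infer that the protocol re-titrates anyone off drug too long and fails to count time on placebo. Figure 2 says "A maximum gap of 28 days is allowed between the end of the Double-Blind Phase" and the start of the extension, and Section 6.1.5 says "De novo subjects may also be subjects who have completed the core study more than 28 days ago". But that wording is permissive. De novo entry requires a stable opioid dose of at least 40 mg morphine equivalents for 14 days before Screening (7.6.1). De novo subjects then "will undergo the same screening procedures, down titration, morphine IR, Buprenex test dose, and CAM2038 up-titration". The route suits people back on daily opioids. It is not a measure of time off buprenorphine.

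**Dissociation time.** A reader might set 91 days against the two weeks in Section 8.7 and infer lost tolerance. That figure concerns how long buprenorphine may blunt the analgesic effect of other opioids.

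**Missing post-dose checks.** A reader might treat the absence of a post-dose ECG or of 6-10 hour checks as a defect specific to placebo completers. De novo subjects also receive their first monthly depot without them (Table 10b), COWS and SOWS measure withdrawal and not over-exposure, and no text links QTcF risk to time off drug. Such checks are optional extras.

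**Conclusion.** The point holds as a minor, cheap safety improvement in the extension. Every rollover restarts at the last titration weekly dose. For placebo completers this comes nominally 91 days after the last active injection, and up to 119 with the permitted gap. On study opioids alone they are below the protocol's own 40 mg definition of opioid-experienced, while the only written reduction follows a poorly tolerated depot.

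This rests on nominal visit timing and on study-supplied opioids alone. The 40 mg definition is a screening criterion, used here as a benchmark for whom the doses were chosen. A subject who uses the 28-day gap may meanwhile have taken other opioids, so the 119-day figure and the rescue cap need not apply to the same person. Actual rescue use, loss of tolerance and the number of placebo completers cannot be obtained from the documents. The randomised comparison is unaffected, because the restart follows the Week 12 endpoint.

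**What to change.** In Sections 6.1.5 and 8.1.7.1 and Table 4, state for all weekly and monthly rollovers, regardless of arm so that the blind holds, that the investigator may choose a lower weekly dose before the first open-label injection. An example is the subject's original 4 or 8 mg start, with weekly step-up to the prior dose. Align Section 8.4 with this. Base the choice mainly on recent total opioid and rescue intake and on clinical judgement. Pre-dose COWS alone is not enough: a low score could mean active drug on board or an opioid-free placebo subject.

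**Cost.** A few sentences and one table note. About 140 extension subjects are planned, de novo included (Section 7), so at most that many are touched. The real downside is brief under-treatment of some active completers: a 32 mg subject given 8 mg drops by 24 / 32 = 75%, and given 4 mg by 28 / 32 = 87.5%, until stepped up. Moving one level a week through 4, 8, 12, 16, 24 and 32 mg takes 4 steps from 8 mg or 5 from 4 mg, and monthly dosing is delayed accordingly. Because the option is permissive, the investigator can keep the full dose where recent intake supports it. A 1-hour ECG at Week 23 and 6-10 hour checks at the first open-label monthly injection may be added, but the fix does not depend on them.
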